Strong evidence suggested that Bmi1 was important to invasive potential and favored to the maintenance and self-renewal of CSCs in several tumor types, including HNSCC [44] [41] [24] [45]. As a stem cell marker, Bmi1 played a key role in the functioning of endogenous stem cells and CSCs [46] [45]. Additionally, it has been found to be related to many other CSC markers such as SOX2 [47], Oct4 [48], Nanog [48], ALDH1[32], ABCG2 [2] and CD44 [49] [50]. **Seo et al., 2011** found a connection between BMI-1 and Sox2 in maintaining self-renewal and identified BMI-1 as a key mediator of Sox2 function [47].

Moreover, recent studies have revealed that Bmi-1 expression was associated not only with the development of oral cancer, but also in patients with oral leukoplakia (LP)[40], oral erythroplakia[32], and oral lichen planus[42]. Furthermore, Bmi-1 overexpression was found in LP, and increased significantly from mild to moderate and severe LP. Consistent results were reported in Kang's research, which showed that Bmi-1 overexpression was observed in preneoplastic oral mucosal tissues, including mild, moderate or severe OED [51]. **Ma L et al., 2013** suggested that Bmi1 may act as a beneficial marker for the recognition of high risk of malignant progression of OLP [42].

Wang et al., 2015 studies have indicated that silencing BMI-1 can decrease the malignant biological behavior of cancer, in addition to the self-renewal and differentiation of CSCs. Therefore, BMI-1 was hypothesized to affect the malignant biological behavior of human tumors by regulating the self-renewal and differentiation of CSCs. In conclusion, BMI-1 might represent a hopeful target for the prevention and therapy of various types of human cancer. Further understanding the molecular mechanism underlying the regulation of BMI-1 in human cancer and CSCs is of extremely huge clinical value [52].

PIRT

P→ Diagnostic validity of Bmi-1 levels in archival paraffin embedded tissue samples of oral dysplasia and squamous cell carcinoma.

I 1 → Expression of Bmi-1 protein level by immunohistochemistry in oral dysplasia and squamous cell carcinoma.

I 2 → Expression of Bmi-1 molecule at RNA level by PCR in oral dysplasia and squamous cell carcinoma.

R→ biopsy embedded in paraffin blocks.

T→oral dysplasia and squamous cell carcinoma.

IV. Research Question:

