Does the expression of Bmi-1 vary from oral epithelial dysplasia to different grades of squamous cell carcinoma at protein and molecular levels? Which one of them is more sensitive and specific for Bmi-1 assessment, the protein or molecular levels?

V. Methods:

Source of data:

Convenient consecutive sampling; it will include all archived blocks in the past 5 years (2012-2017).

Study design: Prospective cohort (In vitro validation study test)

Participants:

The archival paraffin embedded tissue samples which will be included in this diagnostic study are 30 samples of oral dysplasia and squamous cell carcinoma. We will apply a convenient consecutive sampling; it will include all archived blocks in the past 5 years (2012-2017) for this validation study. Excluded are samples of sarcomas or benign tumors or any carcinoma other than squamous cell carcinoma or any other techniques rather than immunohistochemistry or PCR. Samples that fulfilled the eligibility criteria will be included consecutively (consecutive sampling) until the target sample size will be reached. Data regarding Bmi-1 antibody expression in oral dysplasia and different grades of squamous cell carcinoma will be collected prospectively from both the reference and index tests independently.

Predictors:

Biopsy embedded in paraffin blocks was selected as reference standard method to assess the expression of Bmi-1 antibody at protein and RNA levels by immunohistochemistry and PCR respectively.

FIRST , PCR ANALYSIS

According to **Borbély et al 2007** tissue blocks will be prepared as follow:

- 1-** Tissue of 30 microns will be cut from paraffin blocks using scalpel and was put in eppendorf.
- 2-** 200 ml of tissue lysis buffer (ATL) + 0.6 ml of DNAs inhibitors + 10 ml proteinase K will be added to the sample.
- 3-** Sample will be incubated at 55 °C for 20 min.
- 4-** 250 micron of ethanol will be added and the sample will be left for 5min at room temperature.
- 5-** Sample will be collected by micropipette into spin column and will be centrifuged at 8000/ rpm for 1 min.
- 6-** 500 microlitre of wash buffer 1 will be added and the spin column will be centrifuged at 8000/ rpm for 1 min.
- 7-** 500 microlitre of wash buffer 2 will be added and the spin column will be centrifuged at 8000/ rpm for 1 min.
- 8-** 500 microlitre of elusion buffer will be added and the spin column will be centrifuged at 14,000/ rpm for 3 min.

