The data will be obtained using the software (SIS, Germany), which comprise a light microscope (Olympus B \times 60 Japan) capable of performing high speed digital image processing for the purpose of cell measurements. It will be calibrated automatically to convert the measurement units (pixels) produced by image analyzer program into actual micrometer units. In immunohistochemical sections, and by using the image analyzer, five specific fields showing maximum positivity of Bmi-1 expression will be used in each case; the mean of five values of each slide will be calculated and statistically will be analyzed. For each field of immunostained section, a measuring frame of area 1920000 pixels and then the area % will be calculated. The color of immunostaining will be automatically selected according to the positive control sections, converted into grey color then masked the red and white to allow automatic measurements by the computer system. Data obtained will be subjected to statistical analysis using Student-t test.

Since BMI-1 level is measured objectively then no blinding is required.

Sample size

The aim of the current study is to assess the validation of Bmi-1 detection at both protein and molecular levels in oral epithelial dysplasia and oral squamous cell carcinoma as a biomarker for early cancer detection versus biopsy embedded in paraffin blocks. We are going to apply a convenient consecutive sampling; it will include all archived blocks in the past 5 years (2012-2017) about 30 samples.

Statistical analysis methods:

Data will be analyzed using IBM SPSS advanced statistics (Statistical Package for Social Sciences), version 21 (SPSS Inc., Chicago, IL). Numerical data will be described as mean and standard deviation or median and range. Categorical data will be described as numbers and percentages. Correlation analysis will be used. Agreement between both methods will be analyzed with the use of kappa statistics.

References:

1. Nagadia, R., et al., *miRNAs in head and neck cancer revisited*. Cellular Oncology, 2013. **36**(1): p. 1-7.
2. Dalley, A.J., et al., *Expression of ABCG2 and Bmi-1 in oral potentially malignant lesions and oral squamous cell carcinoma*. Cancer medicine, 2014. **3**(2): p. 273-283.
3. Kurihara, K., et al., *Expression of BMI1 and ZEB1 in epithelial-mesenchymal transition of tongue squamous cell carcinoma*. Oncology reports, 2015. **34**(2): p. 771-778.

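### The plan asks which Bmi-1 assay is more sensitive and specific, but no listed analysis estimates or compares sensitivity or specificity

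*Combined protocol and SAP*

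**What the plan says.** The Research Question section has two parts. The first is about expression: "Does the expression of Bmi-1 vary from oral epithelial dysplasia to different grades of squamous cell carcinoma at protein and molecular levels". The second is about accuracy: "Which one of them is more sensitive and specific for Bmi-1 assessment, the protein or molecular levels". The Sample size section gives the aim as validating Bmi-1 detection "as a biomarker for early cancer detection versus biopsy embedded in paraffin blocks".

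The planned analyses are few. The Statistical analysis methods section lists summaries of numerical and categorical data, a correlation with neither type nor variables given, and kappa: "Agreement between both methods will be analyzed with the use of kappa statistics". The Image analysis text adds one test: "Data obtained will be subjected to statistical analysis using Student-t test".

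Three further statements bear on whether accuracy could be computed:

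- PIRT, target: "T→oral dysplasia and squamous cell carcinoma".
- Predictors, reference: "Biopsy embedded in paraffin blocks was selected as reference standard method to assess the expression of Bmi-1 antibody at protein and RNA levels".
- Participants, data collection: "Data regarding Bmi-1 antibody expression in oral dysplasia and different grades of squamous cell carcinoma will be collected prospectively from both the reference" and from the index tests.

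The IHC reading is an area percentage averaged over five fields. The PCR reading is a relative quantification (RQ). Both are continuous, and no positivity cut-off is given for either.

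**The concern.** Sensitivity and specificity require three things: a reference classification of each block, a statement of which class is target-positive, and a rule that turns each reading into positive or negative. Comparing two assays also requires an analysis that sets each against that reference in the same blocks. The plan asks the question but supplies none of these.

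Two things are at stake. A good kappa between IHC and PCR could be reported as validation although it says nothing about how well either assay separates carcinoma from dysplasia, and a poor kappa would not show which assay is at fault. Also, the blocks and readings would still permit an accuracy analysis later, but the target and the cut-offs would then be chosen with the results in view, and the answer would be hard to trust.

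**Working it through.** The plan has no figure to reproduce: its sample size of about 30 rests on no stated accuracy, kappa or precision target. The check takes each listed analysis in turn.

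**1. What each analysis can deliver**

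- Descriptive summaries describe each reading. They do not set it against a reference.
- A correlation measures association. If it is between the two assays, it does not use the diagnosis.
- The Student t-test compares means of the image data. It covers IHC only and gives neither sensitivity nor specificity.
- Kappa is taken below under both readings of the phrase about both methods.

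**2. Kappa between IHC and PCR (the likelier reading)**

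Assumed: 15 carcinoma (OSCC) and 15 dysplasia (OED) blocks, since the plan gives no split, and some cut-off for each assay. Let the IHC-by-PCR table be ++ 12, +− 3, −+ 3, −− 12.

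- Observed agreement: Po = (12 + 12)/30 = 0.80.
- Each assay is positive in 15 of 30, so Pe = (15×15 + 15×15)/30² = 0.50.
- Kappa = (Po − Pe)/(1 − Pe) = 0.30/0.50 = 0.60.

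The same table arises from very different truths (counts in the order ++, +−, −+, −−):

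| OSCC blocks | OED blocks | IHC sens. / spec. | PCR sens. / spec. | Kappa |
|---|---|---|---|---|
| 12, 3, 0, 0 | 0, 0, 3, 12 | 15/15, 15/15 | 12/15, 12/15 | 0.60 |
| 12, 0, 3, 0 | 0, 3, 0, 12 | 12/15, 12/15 | 15/15, 15/15 | 0.60 |
| 6, 2, 1, 6 | 6, 1, 2, 6 | 8/15, 8/15 | 7/15, 7/15 | 0.60 |

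Kappa treats the two assays symmetrically and does not use the diagnosis, so it cannot rank them.

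**3. Kappa of each assay against the reference (the other reading)**

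With the same 15/15 split, Pe = 0.50 whatever the assay's positive rate, because the reference is positive in half the blocks. Po = 24/30 = 0.80 then gives kappa 0.60 for sensitivity 15/15 with specificity 9/15, for 12/15 with 12/15, and for 9/15 with 15/15. One number cannot be separated into the two quantities that the question asks about.

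**4. Whether the inputs to an accuracy analysis are defined**

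- *Cut-off:* none for area percentage or RQ. Kappa, sensitivity and specificity all need one.
- *Reference:* the block is the material on which both assays are run, not a classification of it. The Participants sentence on reference and index tests concerns Bmi-1 expression data, so it does not supply a diagnosis.
- *Target:* read literally, the PIRT target includes both dysplasia and carcinoma. The study includes only those two diagnoses and names no normal-mucosa group, so no block is target-negative and specificity has no denominator.

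**5. Precision once the analysis is added (illustration)**

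Exact (Clopper-Pearson) 95% intervals for an observed specificity of 80%, at a cut-off fixed in advance and with assumed numbers of OED blocks:

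- 12/15: 52% to 96%.
- 4/5: 28% to 99%.

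**The case against.** **The phrase about both methods is ambiguous.** The Participants section also pairs the reference with the index tests, so kappa might be meant for each assay against the reference. That is fair, and on that reading kappa would use the diagnosis and could indicate which assay matches it better overall. It would still give neither sensitivity nor specificity, and it would still lack a cut-off and a usable reference.

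**The question may not be about cancer.** It asks about sensitivity and specificity for assessing Bmi-1, which could mean detecting Bmi-1 itself. The early-detection aim points the other way, but the wording leaves the possibility open. On that reading the plan would need a separate reference for true Bmi-1 status and names none. The gap remains and the sponsor must say which is meant.

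**Stronger readings that the documents do not support.**

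- A reader might infer that no diagnosis exists to serve as reference, or that specificity can never be estimated. Eligibility depends on diagnosis, so each block must have one. The plan fails to name it as the reference, and OSCC versus OED is a contrast the eligible blocks allow.
- A reader might infer that kappa tends to favour the worse pair of assays. It does not when the pairs are compared like for like. With 50% OSCC and equal within-class correlation (bivariate-normal model), two assays at 55% sensitivity and specificity against two at 90% give kappa 0.01 against 0.64 at correlation 0, 0.34 against 0.73 at 0.5, and 0.72 against 0.88 at 0.9. The accurate pair is higher each time. What stands is that kappa cannot show which assay is better, and that poor assays with strongly correlated readings can still agree well.
- A reader might infer that 30 blocks make the accuracy question pointless. The small number argues for reporting intervals and modest conclusions. It does not justify leaving out the analysis.

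**Conclusion.** The point holds and should be fixed before analysis. One of the two research questions has no analysis that could answer it, and the target, reference and cut-offs that such an analysis needs are undefined. This conclusion rests on the plan's own text and on none of the assumed numbers.

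The kappa example assumes a 15/15 split and chosen cell counts. It shows that kappa cannot rank the assays; it does not predict what the study will find. The interval widths likewise rest on assumed splits and a fixed cut-off. The plan gives no value for any of these, so the size of a wrong conclusion cannot be calculated.

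**What to change.** (a) In PIRT and Predictors, name the archived histopathological diagnosis of each block as the reference standard. State observer variation as a limitation; the literature review already acknowledges it for grading dysplasia.

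(b) State before analysis which diagnosis is target-positive and which is the comparator. OSCC versus OED is the contrast the eligible blocks allow. The sponsor must confirm it and limit the conclusion to it. If detection of Bmi-1 itself is meant, name a separate reference for that.

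(c) Add to Statistical analysis methods:

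> For the stated contrast, the ROC AUC of IHC area % and of PCR RQ will be given with 95% CIs, with the paired AUC difference and its 95% CI. If a cut-off is fixed before analysis, sensitivity and specificity will be given with exact 95% CIs and compared between assays in the same blocks by a paired method. If the cut-off is chosen on these data, sensitivity and specificity will be optimism-corrected, with bootstrap intervals that repeat the cut-off selection in each resample, and labelled exploratory.

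The two cases are separated because exact binomial intervals assume a fixed cut-off. They are not valid for one chosen on the same data or for an optimism-corrected estimate.

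(d) Keep kappa at those cut-offs, and the correlation, as secondary agreement measures that do not rank the assays.

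(e) State that with about 30 blocks the comparison is estimation and may not identify the better assay.

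The cost is wording in three places and more analysis on the same blocks, with no new samples or assays. The sponsor should check that the named SPSS version can run the paired AUC comparison and the bootstrap. The claim narrows to one contrast. If OED is the comparator, Bmi-1-positive dysplasia, which the literature review reports, counts as false positive. The intervals will be wide.

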- 4- Serum block: sections will be incubated with normal horse serum blocking solution for 30 minutes to block non-specific binding of immunoglobulin. The best results will be obtained with dilution 1:25. Slides will be rinsed in washing buffer for 2×2 min
- 5- Peroxidase blocking: sections will be incubated in peroxidase blocking solution for 10 minutes to block endogenous peroxidase activity.
- 6- Slides will be rinsed in washing buffer 3×2 min
- 7- Secondary antibody: sections will be incubated with biotinylated horse Anti-Mouse IgG diluted in secondary antibody dilution.
- 8- Slides will be rinsed in washing buffer 3×2 min.
- 9- Chromogen/substrate: sections will be incubated in DAB peroxidase substrate solution for 5-10 min and then will be rinsed with distilled water
- 10- Slides will be counter stained with Mayer's haematoxylin solution, then will be rinsed in running tap water for 5 minutes
- 11- Slides will be dehydrated through 95% ethanol for 2 minutes, 100% ethanol for 2×3 minutes
- 12- Finally, they will be cleared in xylene for 2-3 minutes and cover slipped with permanent mounting medium.

Since BMI-1 level is measured objectively then no blinding is required.

First: Calculation of Relative Quantification (RQ) (relative expression):

After the RT-PCR will run, the data will be expressed in Cycle threshold (Ct).PCR data sheets will include Ct values of assessed gene and the house keeping (reference) gene which will be continuously expressed in the cell- (β -actin).To measure the gene expression of certain gene, -ve control sample shall be used. So target gene expression will be assessed and related to reference (internal control) gene as follows:

Finally, RQ was calculated according to the following equation:

1. ΔCt (Cycle threshold) = Ct assessed gene – Ct reference gene
2. $\Delta\Delta Ct$ = ΔCt sample – Ct control gene
3. $RQ = 2^{-(\Delta\Delta Ct)}$

Second: Image analysis:

In order to provide more précis data on Bmi-1 immunoexpression in OSCC, image analyzer will be used.

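### Kappa is the only agreement measure named, but both assays give continuous values in unlike units and no categories or cut-offs are defined, so it cannot be computed as written

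*Combined protocol and SAP*

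**What the plan says.** The section on statistical analysis methods gives two sentences on comparing the assays: "Correlation analysis will be used" and, directly after it, "Agreement between both methods will be analyzed with the use of kappa statistics". The first names neither the type of correlation nor the variables. The second gives no categories, no type of kappa (unweighted or weighted) and no confidence interval.

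The readouts are defined earlier in the Methods:

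- **IHC** (Second: Image analysis): "For each field of immunostained section, a measuring frame of area 1920000 pixels and then the area % will be calculated". Five fields are read per case, and "the mean of five values of each slide will be calculated and statistically will be analyzed". The section ends with "Data obtained will be subjected to statistical analysis using Student-t test", so the plan itself treats area % as numerical.
- **PCR** (First: Calculation of Relative Quantification): the result is RQ, 2 raised to the power −ΔΔCt, which is a unitless fold value.

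The only mention of categories is the general sentence "Categorical data will be described as numbers and percentages". No threshold, score or grade band for area % or RQ appears anywhere. Positive control sections are used to set the stain colour. That decides which pixels count as stained, not which case counts as positive.

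**The concern.** Kappa compares how two methods place the same samples in the same set of categories. Here one method gives a percentage of area and the other a fold value. Taken as produced, almost every sample would be its own category and the two scales would have none in common. A kappa can be reported only after somebody adds a rule that the plan does not contain.

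Kappa depends strongly on that rule. If it is settled once the readings are known, the reported agreement may reflect where the cuts were placed rather than how well the assays concur. The plan offers no protection through masking, since it says twice that blinding is unnecessary because the level is measured objectively.

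The comparison of the two assays is central. The Research Question asks which level, protein or molecular, is the more sensitive and specific. That question also needs positive and negative calls, so the same gap blocks it.

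**Working it through.** **Is kappa computable from the stated outputs?** The inputs are an area % averaged over five fields and RQ = 2^−(ΔΔCt). Both are continuous and no rule maps either to categories. Kappa, weighted or not, needs common categories, so it is not computable as written. The plan states no expected kappa, precision or power, and its figure of about 30 samples is not derived from any such input. There is therefore no planned figure to reproduce.

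**How much would an unstated cut-off rule matter?** The plan gives no protein–RNA correlation, so the following is an assumed model: the two assay values are bivariate normal on some monotone scale, with correlation ρ of 0.4, 0.6 or 0.8. Only ranks matter, so the units do not. Each assay is cut at a percentile, leaving proportions p1 and p2 positive, and p11 is the probability that both are positive.

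- Observed agreement: po = 2·p11 + 1 − p1 − p2
- Chance agreement: pe = p1·p2 + (1 − p1)(1 − p2)
- Kappa = (po − pe)/(1 − pe)

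| ρ | cuts (percentiles) | p11 | po | pe | kappa |
|---|---|---|---|---|---|
| 0.6 | 50 / 50 | 0.352 | 0.705 | 0.50 | 0.41 |
| 0.6 | 50 / 60 | 0.299 | 0.697 | 0.50 | 0.39 |
| 0.6 | 40 / 60 | 0.333 | 0.665 | 0.48 | 0.36 |
| 0.6 | 50 / 80 | 0.168 | 0.636 | 0.50 | 0.27 |
| 0.6 | 30 / 80 | 0.190 | 0.479 | 0.38 | 0.16 |
| 0.6 | 20 / 80 | 0.196 | 0.391 | 0.32 | 0.10 |
| 0.4 | 50 / 50 | 0.316 | 0.631 | 0.50 | 0.26 |
| 0.4 | 20 / 80 | 0.187 | 0.373 | 0.32 | 0.08 |
| 0.8 | 50 / 50 | 0.398 | 0.795 | 0.50 | 0.59 |
| 0.8 | 20 / 80 | 0.200 | 0.399 | 0.32 | 0.12 |

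The 20/80 rows are low largely by construction. With 80% positive on one assay and 20% on the other, p11 cannot exceed 0.20. So po cannot exceed 0.40, and kappa cannot exceed (0.40 − 0.32)/0.68 = 0.12 even if the two rankings are identical.

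**Worst case under tuning.** The assays are taken as unrelated (ρ = 0) with n = 30, and the cut pair with the highest kappa is picked in each simulated data set. With cuts allowed from about the 20th to the 80th percentile, the mean best kappa is about 0.33 (5th to 95th percentile 0.13 to about 0.55). With cuts confined to about the 40th to 60th percentiles, it is about 0.20. With both cuts fixed at the median, the mean is 0.00, as it should be.

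**Precision once a rule is fixed.** The simple large-sample standard error is √[po(1 − po)/(n(1 − pe)²)]. At ρ = 0.6 with median cuts and n = 30, this is √[0.705 × 0.295/(30 × 0.25)] = 0.17, or about ±0.33 for a 95% interval. Even a well-defined kappa needs its interval reported.

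**The case against.** Four points can be made for the plan.

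- **Cut-offs need not be chosen after the data are seen.** A reader might infer from the silence that they will be, or that this is the only way to get a kappa. The documents do not say so. An externally sourced or control-based threshold could be fixed beforehand, and the plan already uses controls in both assays. This stands: the supportable claim is that the rule is unstated, which leaves the choice open.
- **A correlation is already planned.** A reader might infer that the plan has no cut-off-free comparison of the assays. It has one in outline, in the sentence just before the kappa sentence. But correlation measures association, so kappa remains the only agreement measure, and the correlation is too vague to carry the comparison as it stands.
- **The large effects come from extreme choices.** This is fair. Mild mismatch of cuts costs little (0.36 to 0.39 against 0.41), and the plan does not propose searching for the highest kappa. The low values and the 0.33 are bounds, not expected bias.
- **The two methods are not named in the kappa sentence.** The Participants section also speaks of reference and index tests. IHC against PCR is the likelier reading, given the Research Question, but the sentence should say so.

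None of this supplies the missing categories.

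**Conclusion.** The point holds as a mismatch between the method and the data. The one agreement measure named cannot be obtained from the outputs that the plan defines. That conclusion rests on the text alone and needs no model.

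The size of the effect does rest on assumptions, namely bivariate normality and correlations of 0.4 to 0.8 that the documents do not give. Within them, the placement of cuts can move kappa from 0.41 to 0.10 at a correlation of 0.6, from 0.26 to 0.08 at 0.4, and from 0.59 to 0.12 at 0.8. Those are end-to-end ranges. The tuned null value of about 0.33 is a worst case and should not be read as a forecast of what this study will report. The documents do not support a claim that cut-offs will be tuned, only that nothing prevents it.

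**What to change.** In the statistical analysis section:

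1. State that the two methods compared are IHC and PCR. Specify the planned correlation as Spearman's between area % and RQ, with a 95% CI, as the main between-assay result. Using −ΔCt instead of RQ gives the same ranks if the control term is constant across samples. Call the result association, not agreement. Bland–Altman limits or an intraclass correlation on the raw values would not suit unlike units.
2. Keep kappa as secondary, name its type, and report it with a 95% CI. Fix one rule per assay before any assay is read: preferably a justified positivity cut-off with its source or, failing that, a split at each assay's own median.
3. If the median split is used, label it a convention. It forces 50% positive on both assays, cannot show that one assay calls more cases positive than the other, and cannot answer the sensitivity and specificity question in the Research Question section. That question needs real positivity cut-offs.
4. State that cut-offs will not be tuned on these 30 samples.

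The cost is a few sentences and, if sourced cut-offs are used, the work of justifying them. No new samples or assays are needed. The downside is that the main between-assay result becomes association rather than categorical agreement.

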The acquisition of genetic or epigenetic predisposition to tumorigenicity by CSCs has been shown to be a cumulative process [31] that might be evident in premalignant lesions [32] [33] as well as oral epithelial tumorigenicity [34]. This increased the importance of unraveling the underlying molecular events associated with CSC population, as they could serve as early detectors of malignant potential in OED and prognosis of OSCC. Thus, the signaling pathways required for the maintenance of CSCs became candidate targets of recent investigations in this field. Currently, light was shed on **B-lymphoma Moloney murine leukemia virus insertion region-1** (BMI-1) which has been implicated in the regulation of CSCs.

BMI-1 oncogene is a member of the polycomb-group gene family and a transcriptional repressor. BMI-1 was first recognized in a B-cell lymphoma as a transcriptional repressor that was a member of the P_cG transcription factors [35]. Certain studies have revealed that BMI-1 was involved in the self-renewal, differentiation and tumor initiation of CSCs [36] [37] [25]. Nevertheless, the molecular mechanisms underlying these biological processes remained vague.

In addition, BMI-1 was known to be upregulated in various human cancer tissues and was important in the regulation of malignant transformation, proliferation, cell cycle, apoptosis and distant metastasis [38]. Actually, many studies have reported that Bmi1 was overexpressed in HNSCC cells when correlated to normal epithelium and was thought to impact cell proliferation and survival in HNSCC [39] [40] [41] [42]. **Song et al 2009.**, demonstrated that Bmi-1 mRNA and protein expression levels were found to correlate with the invasion of nasopharyngeal carcinoma [7].

In clinical specimens of HNSCC, many researchers have established that the overexpression of Bmi-1 correlated with poor overall survival [43] [39] [41]. Likewise, **He et al 2015.**, added that the expression of Bmi1 was correlated with poor overall survival and was also associated with lymph node metastasis and clinical stage.

Association of Bmi1 overexpression, and stem-like properties in tumor cells could be attributed to induction of the EMT that promoted invasion, metastasis, and poor prognosis [41]. In the same background, **Yang et al., 2010** showed that BMI1 was necessary for EMT during tumor development in head and neck cancer patients [8].

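### Kappa is the only planned measure of IHC–PCR agreement; in a lesion-only sample with no stated cut-offs it cannot, on its own, separate assay disagreement from a shortage of negative samples

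*Combined protocol and SAP*

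**What the plan says.** The agreement analysis is one sentence, under Statistical analysis methods: "Agreement between both methods will be analyzed with the use of kappa statistics". The type of kappa, any weighting and a confidence interval are not given. Two neighbouring sentences come close to the subject without covering it. "Correlation analysis will be used" names no variables or coefficient, and correlation measures association, not agreement. "Categorical data will be described as numbers and percentages" does not commit to an IHC-by-PCR cross-table or to observed agreement.

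On case mix, the Participants paragraph of V. Methods says: "The archival paraffin embedded tissue samples which will be included in this diagnostic study are 30 samples of oral dysplasia and squamous cell carcinoma". It continues: "Excluded are samples of sarcomas or benign tumors or any carcinoma other than squamous cell carcinoma". No normal-mucosa group is listed.

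Both readouts are continuous. PCR gives a relative quantification (RQ). Under Image analysis, IHC gives a stained-area percentage, averaged over the five fields per case with the strongest Bmi-1 staining. Neither has a threshold for calling a sample positive.

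The literature review reports raised expression in both lesion types: "Bmi-1 overexpression was observed in preneoplastic oral mucosal tissues, including mild, moderate or severe OED" and "Bmi1 was overexpressed in HNSCC cells when correlated to normal epithelium". It gives no percentage of positive specimens.

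**The concern.** Kappa subtracts the agreement expected by chance, which it computes from the proportion each assay calls positive. When nearly all samples fall in one category, expected agreement is close to 1 and kappa becomes low and unstable, even if the two assays seldom differ.

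Three features of the plan make skewed margins plausible. The sample contains lesions only. The background leads one to expect raised Bmi-1 in those lesions. Reading IHC in the strongest fields pushes area % upward, so IHC-negative cases become rarer under any fixed threshold.

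The protein-versus-RNA comparison is part of the research question, and kappa is its only planned agreement result. If kappa came out low, a reader given nothing else could not tell whether the assays disagreed or whether the archive held too few negatives to test them. The value would also depend on a cut-off choice that the plan has not yet made.

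**Working it through.** The documents state no kappa, expected agreement or positivity rate, so there is no planned figure to reproduce. The check shows how far kappa moves with the margins at fixed agreement.

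**Inputs.** From the documents: n = 30 (Participants; described as approximate under Sample size). Assumed: binary categories, 27/30 agreement, and a range of positive rates.

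**Formulas.** Let a = both positive, b and c = the two discordant cells, d = both negative.
- Observed agreement: po = (a + d)/n = 27/30 = 0.900 (Wilson 95% CI 74% to 97%)
- Chance agreement: pe = [(a+b)(a+c) + (c+d)(b+d)]/n²
- Kappa = (po - pe)/(1 - pe)
- Positive agreement = 2a/(2a+b+c); negative agreement = 2d/(2d+b+c)

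**Worked example, 27/2/1/0.** pe = (29×28 + 1×2)/900 = 814/900 = 0.904. Kappa = (810 - 814)/(900 - 814) = -4/86 = -0.05. Positive agreement = 54/57 = 94.7%. Negative agreement = 0/3 = 0%.

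**All tables below have 27/30 agreement** (large-sample CIs; upper limits above 1 shown as 1.00):

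| a/b/c/d | Mean % positive | pe | Kappa (95% CI) | Positive agreement | Negative agreement |
|---|---|---|---|---|---|
| 27/2/1/0 | 95.0 | 0.904 | -0.05 (-0.11 to 0.02) | 94.7% | 0% |
| 26/2/1/1 | 91.7 | 0.847 | 0.35 (-0.22 to 0.92) | 94.5% | 40.0% |
| 25/2/1/2 | 88.3 | 0.793 | 0.52 (0.04 to 0.99) | 94.3% | 57.1% |
| 24/2/1/3 | 85.0 | 0.744 | 0.61 (0.21 to 1.00) | 94.1% | 66.7% |
| 21/2/1/6 | 75.0 | 0.624 | 0.73 (0.45 to 1.00) | 93.3% | 80.0% |
| 14/2/1/13 | 51.7 | 0.500 | 0.80 (0.59 to 1.00) | 90.3% | 89.7% |

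Putting all three discordant samples on one side changes little: kappa is then 0.00, 0.37, 0.53, 0.62, 0.74 and 0.80 down the rows.

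**Equal margins.** With proportion p positive on both assays and po = 0.90, pe = p² + (1-p)². At p = 0.95, kappa = (0.90 - 0.905)/0.095 = -0.05. At p = 0.90, it is (0.90 - 0.82)/0.18 = 0.44. At p = 0.75, it is (0.90 - 0.625)/0.375 = 0.73. At p = 0.50, it is 0.40/0.50 = 0.80.

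**Two readings of the table.** Moving one sample from double positive to double negative (first row to second) shifts kappa by about 0.39, with raw agreement unchanged. The narrow interval in the first row comes from the empty cell and is not real precision: with one double negative the interval runs from -0.22 to 0.92.

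**The case against.** The strongest objection is that the premise is not in the documents. A reader might infer that nearly all samples will be positive and that kappa will therefore misreport agreement. The text does not support this. Overexpression relative to normal epithelium is a statement about groups, not a positivity rate. The same review links higher expression to worse survival and stage, and reports an increase with the severity of leukoplakia; both require variation between specimens. The research question itself asks: "Does the expression of Bmi-1 vary from oral epithelial dysplasia to different grades of squamous cell carcinoma at protein and molecular levels". This part of the objection stands, and the point is conditional.

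A reader might also infer that the problem arises under any cut-off that does not split the sample near half. That is wrong. At 75% positive, kappa is still about 0.73 and at 85% about 0.61. At n = 30 with 27 agreeing, a value near zero needs no sample negative by both assays.

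Nor is a near-zero kappa in that corner necessarily misleading. Two unrelated assays that each call 95% positive would agree in 0.95² + 0.05² = 90.5% of samples, so kappa rightly says that 90% is no better than chance. It would therefore be a mistake to make overall agreement the main result and demote kappa.

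Finally, kappa cannot be computed at all until RQ and area % are categorised. That is a more basic gap, but closing it does not remove this one: a cut-off for overexpression applied to lesions only can still give skewed margins.

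**Conclusion.** The point holds as a conditional risk that the plan should address. Kappa is the only agreement measure, the sample is lesion-only, and the margins are uncontrolled because no cut-off is stated. If the cut-offs make about 90–95% of samples positive, kappa at 27/30 agreement lies between about -0.05 and 0.4, against about 0.73 at 75% positive and 0.80 at 50%. In that range kappa alone cannot separate disagreement between assays from a sample with too few negatives to judge.

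This rests on assumptions outside the documents: binary calls, 90% agreement, and the positive rates shown. The documents do not establish that skewed margins will occur or that kappa would be wrong if they did. What they establish is that the planned report would leave a low value uninterpretable.

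**What to change.** Keep kappa and report it with a 95% CI. Fix the positivity cut-offs for RQ and area % before analysis; without them there is no table to report. Then add to Statistical analysis methods:

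> *The IHC-by-PCR 2x2 table will be reported with kappa, together with overall agreement and the symmetric positive and negative agreement indices (2a/(2a+b+c) and 2d/(2d+b+c)) with 95% CIs; conclusions on agreement will not rest on kappa or on overall agreement alone.*

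The symmetric indices do not require either assay to be named as the reference. In the 27/2/1/0 example they would show 94.7% positive and 0% negative agreement beside a kappa of -0.05, so the reader would see that no sample was negative by both assays.

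Once the cut-offs are set, the cost is one sentence and a few extra figures from the same table, with no new data. The drawback is that negative agreement will be imprecise if few samples are negative; the reported interval and counts should make that visible.
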